**Table 3. Sample size calculations**

		PARAMETER
Minimum Detectable Effect Size (MDES)		0.17sd
Pre-test/ post-test correlations	level 1 (participant)	0.5
	level 2 (cluster)	0
Intracluster correlations (ICCs)	level 1 (participant)	0
	level 2 (cluster)	0

		PARAMETER
Alpha 		0.05
Power		0.8
One-sided or two-sided?		Two
Number of participants	Intervention	425
	Control	425
	Total	850

## 4 Outcome measures

Outcomes data will be collected at two time points - baseline (prior to randomisation) and again 12 weeks later – focused on measuring the impact of mentoring on socio-emotional learning (SEL), using young people’s self-report. SEL was selected as the appropriate short-term outcome measure, aligned with the mentoring approach outlined in the theory of change to improve prosocial behaviours, confidence, and self-efficacy.

### 4.1 Primary outcome

The primary outcome measure for the efficacy trial, as for the feasibility trial, will be the **Strengths and Difficulties Questionnaire (SDQ)**, a core measure of SEL included in most YEF evaluations.

The SDQ is a validated scale with an established evidence base which measures behaviours, emotions, and relationships across 25 items. As with the feasibility trial, the efficacy trial will adopt the self-report version, suitable for 11- to 17-year-olds. It includes five subscales, each with five items, that measure: 1. Emotional symptoms; 2. Conduct problems; 3. Hyperactivity/inattention; 4. Peer problems; 5. Prosocial behaviour. Young people score from

---

 Please adjust as necessary for trials with multiple primary outcomes, 3-arm trials, etc., when a Bonferroni correction is used to account for family-wise errors.

 Goodman, R (2001) *Psychometric properties of the strengths and difficulties questionnaire*. *Am Acad Ch Adolesc Psychiatry* 40 (11) 1337-45.

 Parent/carer and teacher versions are also available.

0 to 2 on each item using a scale 'not true', 'somewhat true' or 'certainly true', thus producing a score for each subscale from 0 to 10, where a lower score is a better outcome. The primary outcome in the analysis of the efficacy trial will be the mean of an overall 'difficulties' score (from 0 to 40), calculated by summing the first four subscales. Exploratory analysis will include the use of the SDQ four-group categorisation of need, the five subscales and internalising and externalising problems (based on combinations of different subscales, scored from 0 to 20), known to provide intermediate risk and protective factors of offending.

The findings from the feasibility trial suggests that the efficacy trial is highly unlikely to identify statistical significance impacts after 12 weeks on young people's SDQ score, with movement on the SDQ domains likely to take longer to achieve. However, its inclusion in the efficacy trial will allow for a test of the feasibility of fielding the YEF core measure within a multisite trial (including those which may have longer follow-up periods than 12 weeks).

## 4.2 Secondary outcomes

Four **secondary outcome measures will measure shorter-term SEL outcomes, with the questions being taken from previous evaluations of the National Citizen Service (NCS).** These items have been chosen as likely to reflect changes in outcomes after 12 weeks of mentoring.

The decision to use the NCS items is based on (a) the face validity of the items, which speak directly to our Theory of Change and to the 12-week outcomes reported by mentors and mentees in the feasibility trial (including improved confidence, problem-solving, decision making, and emotional regulation), and (b) whilst not validated, their proven sensitivity in other studies to change over a three-month period. We will include 21 NCS items which, between them, cover the following belief-based domains: (a) self-confidence: leadership and communication; (b) problem-solving and decision-making skills; (c) teamwork and social skills building; (d) resilience/emotional regulation. Seven items use a five-point confidence scale, from 'very confident' to 'not at all confident', while the others use a five-point Likert scale ('strongly agree' to 'strongly disagree'). Although the NCS evaluations have reported separately on the impact on each item, we will use factor analysis to produce three separate outcomes, one per domain. Exploratory analysis will include looking at the individual items. The full list of items is included in Appendix 5.

---

 The latest published report is Fitzpatrick et al (2021): [https://assets.publishing.service.gov.uk/government/uploads/system/uploads/attachment\\_data/file/1015222/NCS\\_2019\\_Evaluation\\_Report.pdf](https://assets.publishing.service.gov.uk/government/uploads/system/uploads/attachment_data/file/1015222/NCS_2019_Evaluation_Report.pdf)

 The NCS evaluations (adopting a quasi-experimental design) identified a range of statistically significant impacts across these domains three months after starting an NCS programme. A number of these items also identified significant impacts after 12 weeks in the QED evaluation of the Youth Investment Fund: <https://npproduction.wpenginepowered.com/wp-content/uploads/2021/05/The-Youth-Investment-Fund-Learning-and-Insight-Paper-Seven.pdf>

### **4.3 Services as usual**

Data on the services received by the control group and the non-mentoring services received by the intervention group will be collected through an online form completed by mentors at the 12-week follow-up point. This will cover whether any of a list of service types was provided and the total number of hours of support provided.

### **4.4 Methods and data collection**

An online data portal has been developed to capture all of the quantitative trial data.

The outcomes data will be collected via an online self-completion survey hosted by the evaluation team, with the baseline survey completed prior to randomisation and the follow-up survey completed 12 weeks later (with flexibility to 16 weeks to maximise response rates). For the control group, follow-up outcomes must be collected prior to them starting mentoring.

For each survey (baseline and follow-up), young people will be sent an email by the DPO with a link to the online survey. Depending on capability and/or internet access, this can be completed on a personal device (smartphone, computer, etc.) or at the DPO. To facilitate full and accurate data collection, we will recommend that DPO staff or a parent/carer provides support to any young people unable to complete the survey on their own. However, answers must be made independently and confidentially. Guidance for DPO staff on how to administer the young people's survey and to provide appropriate support is included in the Delivery Handbook provided. For the efficacy trial, the survey will be programmed to allow young people to skip any question they would prefer not to answer. Part of the evaluation of the efficacy trial will be to explore the acceptability of the measures based on the level of missing data.

DPOs will be responsible for monitoring whether a young person has completed the baseline and follow-up measures, using information on the portal about whether a survey has been completed and submitted. However, documentation provided to young people will make clear that DPOs have no access to their responses, which are only accessible to the research team for evaluation purposes. Because completion of the baseline measures is a prerequisite to entering the trial, there will be 100% completion of these (albeit with the potential for some missing data, as described above). At the follow-up stage, there is a target of at least 90% or completion in both arms of the trial. Experience from the feasibility stage suggests that achieving the baseline and follow-up completion rates will require a substantial amount of monitoring and chasing by DPOs (and monitoring and chasing of DPOs by the evaluation team).

Information about young people's demographic characteristics will be collected through an online form completed by the mentor at baseline. This includes age, gender, whether gender is the same as sex assigned at birth, LGBTQ+, ethnicity, looked after child status, FSM, SEND, and referral route.

Other programme administrative data collected includes adherence to trial procedures and the shared practice model, frequency and duration of mentoring sessions per young person, and other services received (for both intervention and control groups). This will be provided by DPOs at 12 weeks from randomisation for each young person. DPO managers will be given a framework of data types at the start of the evaluation to ensure this information is routinely collected.

**Table 4. Methods overview**

Research methods	Data collection methods	Participants/ data sources (type, number)	Data analysis methods	Research questions addressed
Baseline and follow-up outcomes survey	Online survey	Baseline n=850 young people entering the trial, follow-up minimum target n=765 (90%)	Regression-based assessments of impact	Data collection completeness and consistency; Estimates of effect sizes
Young person demographics	Collected and recorded on the portal by DPOs per young person at baseline	850	Descriptive analysis of the two trial arms; covariates in regression analysis	Data collection completeness and consistency; Adherence to randomisation
Programme administrative data	Recorded on the portal by DPOs per young person	850	Descriptive analysis	Adherence to randomisation  Services as usual received

## 4.5 Compliance

DPOs' compliance with the trial requirements will be supported as described above, and particularly through regular one-to-one contacts between the evaluation team and each DPO. DPOs' recruitment of young people, consent processes and the completion of baseline data, mentoring sessions and outcomes data will be monitored through the data portal, with direct contact with each DPO to address any issues of non-compliance.

Fidelity will be assessed both quantitatively and qualitatively at an organisational level. We will collect data on five key criteria:

- Dosage
- adherence to target population
- quality relating to mentor (e.g., consistency of mentor, mentor training)
- quality relating to mentoring components (e.g., initial meeting, written plan, closure process)
- quality relating to interaction (e.g., trusting relationship, safe space, goal setting)

Specific fidelity criteria will be set and assessed, and these assessments combined in a composite fidelity score. DPOs scoring 60% or above will be rated as delivering with medium fidelity, and DPOs scoring 80% or above will be rated as delivering with high fidelity.

This scoring will rely on data from various sources of the evaluation:

- Administrative data: Each organisation will provide administrative data which will include the dates, number and duration of sessions delivered to each young person, consistency of mentor-mentee relationships, and initial meetings.
- Young person profile: We will use the young person profiles to establish whether the young people recruited are eligible for the trial.
- Mentor survey: Mentor survey data will provide information regarding the training that mentors receive.
- Mentee survey: Mentee surveys will be used to establish fidelity to several of the core practice elements of the shared practice model.
- Interviews with managers, mentors and mentees will provide further insight into the extent to which DPOs could deliver in line with the shared practice model, and the challenges they face while doing so.

Additionally, we will collect data on the services received by the control group while on the waiting list in order to establish whether there is extensive contamination between the groups.

## 4.6 Analysis – impact evaluation

The analysis of the trial data will be on an intention-to-treat basis. Estimates of impact per outcome will be regression-based, with baseline outcomes entered as covariates. Organisation will be entered as a fixed effect. The primary analysis will be based on aggregated data from across all sites. Impacts will be presented as Glass's Delta effect sizes.

We will include interaction terms (intervention by organisation) in the model to test whether impacts vary across organisations as an exploratory analysis. It is possible that we conclude from the analysis that there is between-organisation variation in effectiveness. If we find evidence of between DPO differences we will report the impact estimate for each DPO graphically, but not undertake pair-wise tests. It is possible that we conclude from the main analysis that there is between-organisation variation in effectiveness. If we do identify variation, we will undertake exploratory regression analysis to gain an understanding of what is driving those differences. These analyses will consider the following factors:

- location of provision (i.e., school-based v other)
- the profile of young people (in terms of demographics and baseline scores)
- attrition rates
- compliance amongst the intervention group

Exploratory analysis will be undertaken to establish whether there is evidence of sub-group differences in the efficacy of mentoring: by gender, and ethnic group. This will be a descriptive analysis without formal testing of differences (for which the trial is underpowered). The effect sizes per sub-group will be generated via a regression model with interaction terms (randomisation group by sub-group) added. This exploratory work will be presented alongside any qualitative research findings on sub-group differences.

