Support	
1. DPOs will have a written programme plan to guide the 12+ week mentoring relationship
 
2. Key quality dimensions are intentionally attended to through the mentoring relationship
 
 
• Young people feel able to trust their mentor
 
• Relationships between mentors and mentees are high-quality
 
• Spaces where mentoring takes place are emotionally and physically safe
 
• With the support of their mentor, young people set and review goals
 
 
3. Young people have the same mentor for the 12+ week period
 
4. A 'mentoring session' is a minimum of 45 minutes long and includes discussion relevant to the mentoring programme and young person's goals
 
5. Over the 12+ week period, there should be a minimum of twelve sessions
 
6. If the mentoring is extended beyond twelve weeks, reasons should be documented
 
7. Mentors will be supported throughout the mentoring programme by a line manager, for practice development and resolution of risks and issues
 
8. Mentoring will predominantly be delivered in face-to-face sessions although a minority of sessions can be delivered online where appropriate
 
9. Mentoring can take place in any setting, providing it is conducive to a minimum 45 duration mentoring session

Closure	
1. DPOs will have a closure process that includes giving notice of closure to the young person and agreeing it in advance of the final session, and reviewing any scope and boundaries for post-mentoring contact

	
 
2. Closing documentation is issued to the young person at the final session clearly communicating that mentoring has finished
 
3. Early withdrawal or exit is recorded along with any known reasons and relevant mentor reflections
 

--	---

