### 3.5 Sample size calculations

As shown in Table 3., each DPO will have a target of recruiting and randomising 50 young people and delivering mentoring to them, with 50 being set as a challenging, but achievable, number. The expectation is that, across all the DPOs, this will give a trial of around 850 young people, around 425 per arm. Assuming that follow-up data collection is achieved with around 90% this will give an analysis dataset with around 382 per arm. (Follow-up data collection was achieved for 85% of young people taking part in the feasibility trial, but for an efficacy trial we will aim to increase this to at least 90%.)

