shared practice model, quality of mentoring, and acceptability of the trial and shared practice model to young people. The survey will be kept short and at an appropriate reading level, to enable full engagement from young people. Mentees will be able to complete the survey independently or with support from an adult but reassured that their responses are confidential.

**In-depth interviews with DPO managers, mentors, and mentees:** Interviews will be conducted by phone or online video platform and recorded on encrypted recording devices.

One manager from each DPO (total n=17) and 1-2 mentors from each DPO (total n=25) will be interviewed towards the end of the delivery period. We will select the mentor in organisation who has mentored the largest number of young people. In DPOs that did not take part in the feasibility trial we will additionally select the mentor who has mentored the next largest number in the trial.

Interviews will be used to assess the feasibility, acceptability, and appropriateness of the trial arrangements and shared practice model, as well as the key implementation barriers and facilitators faced by DPO staff. We will explore successes, challenges and mitigations faced in recruitment, young people's engagement, leadership, staff, and organisation buy-in, support required by DPOs, the shared practice model, and data collection procedures. Topic guides will be adapted from the feasibility study guides.

25 young people will be selected and interviewed shortly after completion of their mentoring to prevent interference in the mentoring relationship. We will recruit young people through their mentors. We will ask mentors to approach all mentored young people (excluding only those who they judge might be upset by such an approach and including young people who have been less engaged or stopped mentoring before 12 weeks) and invite them to indicate interest in being interviewed. We will develop a purposive sampling framework to inform our selection of young people for interviews, drawing on administrative data, although we anticipate there may be little scope for selection. Sampling criteria will include age, gender, ethnicity, care and SEN-D status, duration of mentoring and risk factors identified in screening.

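### The impact model and the stated MDES leave out clustering by mentor, which arises in the intervention arm only and is not absorbed by DPO fixed effects

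*Protocol*

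**What the plan says.** Section 4.6 describes an intention-to-treat regression for each outcome with baseline outcomes as covariates, and adds: "Organisation will be entered as a fixed effect". It names no mentor term and no clustering of standard errors. Mentor is also absent from its list of factors to explore if impacts vary between DPOs.

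Table 3 gives an MDES of 0.17 SD (two-sided alpha 0.05, power 0.8, participant-level pre/post correlation 0.5) with the ICC at zero at both levels. It shows 425 per arm. Section 3.5 says that "this will give a trial of around 850 young people, around 425 per arm" and, after 10% loss, that "this will give an analysis dataset with around 382 per arm".

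Other sections describe how mentees are grouped:

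- Table 1 (Support): "Young people have the same mentor for the 12+ week period".
- Section 5.2, on choosing mentors for interview: "We will select the mentor in organisation who has mentored the largest number of young people". So at least some mentors carry several mentees. The same section leaves the number of mentors undetermined.
- Section 10: 25 intervention-arm young people per DPO.
- Section 4.4: controls give follow-up data before they start mentoring.

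**The concern.** The intervention is a relationship with one adult. If some mentors achieve more than others, young people who share a mentor have correlated outcomes. Controls have no mentor at follow-up, so the correlation exists in one arm only (a partially nested design). A DPO fixed effect removes what both arms of a site share. It does not remove differences between mentors within that site's intervention arm.

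The protocol's theory of change (section 2.3) makes the quality of the mentor relationship a mechanism of effect and expects mentors with more organisational support to achieve more. Part of that variation lies between DPOs, but nothing in the protocol justifies setting the part within DPOs to zero. At stake are the width of the confidence intervals, the 5% test for every outcome, and the MDES.

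**Working it through.** **Inputs from the protocol.** Table 3: alpha 0.05 two-sided, power 0.8, pre/post correlation 0.5, 425 per arm. Section 3.5: 382 per arm analysed.

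**Assumptions.** Mentees per mentor m = 3 to 12.5; the upper end is 25 per DPO shared by two mentors. Mentor ICC ρ = 0.02 to 0.10, meaning the share of intervention-arm residual variance that mentors cause within a DPO.

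**Step 1: the plan's own figure.** The residual SD after baseline adjustment is √(1 − 0.5²) = 0.866, and MDES = (1.960 + 0.842) × 0.866 × √(2/n).

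- n = 425: 0.166, which rounds to the stated 0.17.
- n = 382: 0.176, with 77.4% power at 0.17.

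The step from 0.17 to 0.176 therefore comes from attrition. It is not a clustering effect.

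**Step 2: partial nesting.** The intervention-arm variance is multiplied by DE = 1 + (m − 1)ρ and the control-arm variance by 1. With equal arms, the ratio of true to planned SE is R = √[(DE + 1)/2]. The MDES is multiplied by R, and type I error is 2[1 − Φ(1.960/R)].

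Example, m = 12.5 and ρ = 0.05: DE = 1 + 11.5 × 0.05 = 1.575; R = √1.2875 = 1.135; MDES = 0.1756 × 1.135 = 0.199.

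Results at 382 per arm:

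| Mentor ICC | Mentees per mentor | R | MDES | Power at 0.17 | Type I error |
|---|---|---|---|---|---|
| 0 | any | 1.00 | 0.176 | 77% | 5.0% |
| 0.02 | 3 | 1.010 | 0.177 | 77% | 5.2% |
| 0.02 | 12.5 | 1.056 | 0.185 | 73% | 6.3% |
| 0.05 | 3 | 1.025 | 0.180 | 75% | 5.6% |
| 0.05 | 5 | 1.049 | 0.184 | 74% | 6.2% |
| 0.05 | 8 | 1.084 | 0.190 | 71% | 7.1% |
| 0.05 | 12.5 | 1.135 | 0.199 | 67% | 8.4% |
| 0.10 | 3 | 1.049 | 0.184 | 74% | 6.2% |
| 0.10 | 12.5 | 1.255 | 0.220 | 58% | 11.8% |

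The top caseload counts randomised mentees. After 10% loss it is 12.5 × 0.9 = 11.25, which gives R = √[(1 + 1.5125)/2] = 1.12 at ICC 0.05.

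**Step 3: simulation.** The planned model (DPO fixed effects and baseline by ordinary least squares) was simulated with 17 DPOs, about 23 v 22 young people per DPO, and 4,000 runs per scenario. With two mentors per DPO, type I error was 4.7% at ICC 0, 6.4% at 0.02, 8.2% at 0.05 and 11.5% at 0.10. With five per DPO at ICC 0.05 it was 6.9%. This agrees with the formula.

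**The case against.** **The zeros in Table 3.** A reader might infer that every zero ICC there is wrong. The protocol does not support that. Young people are randomised individually, 50:50 within each DPO, and DPO is in the model, so a zero at DPO level is acceptable. Only the omitted mentor level matters.

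**Certainty.** A reader might also infer that the standard errors are definitely too small. That needs a positive mentor-caused ICC and caseloads above one, and the protocol gives a figure for neither. At ICC 0.02 with three mentees per mentor the effect is about 1%.

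**Target of inference.** If mentoring affects nobody, there are no mentor effects and the test holds its 5%. Inflation arises when mentors' effects differ but average zero, and when the conclusion is meant for mentors beyond those taking part. Conditioning on the participating mentors can be defended, as it can for organisations. But a trial that asks about the impact of short-term mentoring invites the wider reading, and the protocol does not restrict it.

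**Matching.** Table 1 has DPOs consider mentor-mentee matches, so mentees are not assigned to mentors at random. An observed mentor ICC may partly reflect sorting of similar young people, which does not inflate the variance of the arm mean. In a simulation with sorting-induced ICC of about 0.05 to 0.11 and no mentor effect, type I error was 4.7% to 6.0%. This stands: the formula applies to mentor-caused variance only, and a correction may be somewhat conservative.

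**The SAP.** It was not available here and may specify clustered standard errors. If so, section 4.6 and Table 3 still need to be brought into line with it.

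**Conclusion.** The point holds as a conditional one. The stated model and the MDES omit a source of clustering that the protocol's own design creates in one arm, and DPO fixed effects do not remove it. The planned standard errors are too small if outcomes vary by mentor within a DPO and conclusions are to extend beyond the participating mentors. On the assumed caseloads and ICCs the consequence runs from negligible to material.

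A reader might attribute the whole distance from 0.17 to about 0.20 to clustering. Attrition accounts for the first 0.006 (0.176 − 0.170). At ICC 0.05, clustering adds from 0.004 (0.180 − 0.176) to 0.023 (0.199 − 0.176).

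**What to change.** **Section 4.6.** Keep baseline outcomes and DPO fixed effects, and account for mentor in the intervention arm only. Use either a partially nested mentor random effect or mentor-clustered standard errors, with each control and each unmatched mentee as a singleton. Specify small-sample degrees of freedom: two mentors per DPO would give only 17 × 2 = 34 mentors, and in simulation clustered errors brought type I error back to about 6%, not fully to 5%.

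**Data.** Confirm that the portal records a mentor identifier for each mentee. Section 2.2 mentions mentor and mentee profiles, and section 4.5 mentions data on the consistency of the pairing. These imply a link but do not state one.

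**Table 3.** Give the MDES at the analysed 382 per arm, over a stated range of mentor ICC and caseload.

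**Cost.** A few sentences and a small change to the analysis code. Intervals may widen slightly, the stated MDES becomes a little less favourable, and matching may make the correction somewhat conservative. If the mentor ICC is near zero, the results barely change.
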